14. END-POINTS

Endpoints will include spontaneous passage rate during the 30-day expectant management period or completion of the expectant management period without a requirement for surgery. Secondary endpoints will include ureteral pain during the expectant management period (Visit 1, Interim Follow-up #1 and #2, Visit 2) and pain with a ureteral stent in place (Visit 4).

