9. PROCEDURES

Visit 1 – Emergency Department

In the ED, the subjects will receive a full history and physical, blood tests (including CBC and BMP), urinalysis and culture, urine pregnancy test, CT scan or Ultrasound/KUB of the abdomen

and pelvis, and KUB as part of standard of care for ureteral colic. The radiology department will note on all imaging the largest diameter of the stone and the Hounsfield units. Research study staff will screen potential subjects in the ED by reviewing their charts and will obtain written and verbal consent (in Spanish when necessary) from subjects who meet all inclusion and exclusion criteria. Baseline data, including demographics, medical and surgical history, and current medications, will be collected before randomization.

Each subject will be assigned a unique, consecutive three-digit identification number (i.e., 001, 002...). The study number will be utilized for identification of the subject throughout the study. The clinical study coordinator of the trial will maintain the code that links the name of the participant to their study identification number. The study coordinator will maintain the code in a secured cabinet and the code will be kept confidential. Only the clinical study coordinator and Principal Investigator (PI) can access and view the codes.

Subjects will be asked to complete the Wong-Baker FACES pain scale (available with validated Spanish translation as well). Subjects will be discharged from the ED with a (1) 60 day prescription for the study drug (mirabegron or placebo) (2) urine strainer (3) 60 day log for recording medication adherence, narcotic/analgesic usage, and ureteral pain. Subjects will be instructed to take one pill per day beginning immediately and continuing until they have completed all pills or until they have been instructed to discontinue by the study staff.

Subjects will be provided instructions for use of the urine strainer and collection of any stone or stones that may be passed. They will be instructed to bring any stones that have been passed to the next clinic visit.

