13. DATA ANALYSIS

Patient demographics and clinical characteristics will be summarized by means with standard deviations, medians with minimum and maximum values, or frequencies with percentages. Summary statistics will be stratified by treatment group. No univariable analysis will be completed in this randomized clinical trial.

The primary analysis will compare the proportion of subjects with spontaneous stone passage within 30 days between study groups using Fisher's exact test. Statistical significance will be assessed at the 0.05 level (two-sided). A logistic regression model will also be used to estimate the odds ratio for spontaneous stone passage in the mirabegron group versus the placebo with a 95% confidence interval.

A multiple logistic regression model, adjusting for treatment group, will also be used to test for significant associations between spontaneous stone passage and patient demographics or clinical characteristics. Parameter estimates significant at the 0.05 level will be included in the final multiple regression model. No adjustments will be made for multiple hypothesis testing.

A secondary objective of this study is to compare pain measures between treatment groups. The Wong Baker FACES pain scale will be measured daily for each patient. A general linear mixed model will be used to compare pain scores between treated and placebo groups. The model will include fixed effects for treatment group, time (discrete) and a group-time interaction term. The matrix of correlated residual terms will assume an unstructured format. This model will account for the correlation between repeated measures within the same subject and will allow for all available data to be included in the model.

Missing data will not be imputed. Model fit will be assessed using influence diagnostics and residual analysis. Data transformations (e.g., natural logarithm) will be used if departure from model assumptions is evident. The model will also be used to explore associations between pain scores and demographic and clinical characteristics, adjusting for treatment group and time.

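### The Visit 1 pain score is in effect pre-dose but is listed as an endpoint time, and the planned pain model gives it no baseline role

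*Combined protocol and SAP*

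**What the plan says.** Section 14 (End-points) gives the times of the first secondary endpoint as "ureteral pain during the expectant management period (Visit 1, Interim Follow-up #1 and #2, Visit 2" and so puts Visit 1 on the same footing as the three later contacts.

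Section 9 (Procedures, Visit 1) gives the order of events in the emergency department. First, "Subjects will be asked to complete the Wong-Baker FACES pain scale". Next, "Subjects will be discharged from the ED with a (1) 60 day prescription for the study drug". Then, "Subjects will be instructed to take one pill per day beginning immediately". The same section lists what counts as baseline: "Baseline data, including demographics, medical and surgical history, and current medications, will be collected before randomization". Pain is not in that list.

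Section 13 (Data Analysis) states that "The Wong Baker FACES pain scale will be measured daily for each patient" and describes a general linear mixed model: "The model will include fixed effects for treatment group, time (discrete) and a group-time interaction term". On covariance it says "The matrix of correlated residual terms will assume an unstructured format". It also says that missing data will not be imputed. The example covariates in Section 12 do not include baseline pain.

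**The concern.** At Visit 1 the randomised arms can differ in pain only by chance, because no study drug has been taken. That score is therefore a baseline, and a useful one: it is already collected and measures the same quantity as the outcome. The plan treats it as an outcome time instead.

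Two things are at stake. First, with complete data, a post-dose group contrast from a model with group, time and group-by-time terms is simply the difference in raw means at that time. A chance imbalance in presenting pain passes into it in proportion to the correlation, and the precision that adjustment would give is forgone. Second, Section 13 does not say which contrast tests the treatment. If the group effect averaged over the listed times is used, one of those times can show no effect and pulls the average towards zero.

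**Working it through.** **What the plan gives.** No effect size, SD or within-subject correlation is stated for pain, so there is no planned pain figure to reproduce. The only sizing is for the primary endpoint (Section 11), and it holds up: Fisher's exact test at 0.50 versus 0.80 with 45 per group has exact power of 81.5% against the stated 80%, and 45 × 1.15 = 51.75, rounded up to 52 per group, gives 104. The 45 per group is used below only as a scale.

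**Assumptions.** Equal SD at every time (set to 1), the same correlation r between any two scores (compound symmetry), no effect at Visit 1, and a constant effect d at each post-dose time.

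**Step 1: is Visit 1 pre-dose?** No sentence says so outright. The order in Section 9 (score, then drug supply, then instruction to begin) implies it. Appendix A agrees: medication accountability and adverse-event collection start at Interim Follow-up #1.

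**Step 2: gain from baseline adjustment.** For a contrast at one post-dose time, adjustment multiplies the variance by 1 − r².

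| r | 1 − r² | Variance reduction |
|---|---|---|
| 0.2 | 0.96 | 4% |
| 0.3 | 0.91 | 9% |
| 0.5 | 0.75 | 25% |
| 0.6 | 0.64 | 36% |

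**Step 3: dilution, if the average over all listed times is tested.** With four contacts the average effect is (0 + d + d + d)/4 = 0.75d. The mean of m scores has variance (1 + (m − 1)r)/m. The multiplier on the number of subjects, relative to the mean of the three post-dose contacts, is therefore

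(4/3)² × [(1 + 3r)/4] / [(1 + 2r)/3] = (4/3)(1 + 3r)/(1 + 2r).

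This is 1.52 at r = 0.2, 1.58 at 0.3, 1.67 at 0.5 and 1.70 at 0.6.

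With 30 daily post-dose scores plus Visit 1, the average is 30d/31 = 0.968d.

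**Step 4: the same in power.** Set d so that the three-contact post-dose mean has 80% power at 45 per arm, two-sided 0.05. The standardised effect is then 1.96 + 0.84 = 2.80. Worked case at r = 0.3: the SE ratio is √(0.475/0.5333) = 0.944; 2.80 × 0.75/0.944 − 1.96 = 0.27, and the power is 60.5%.

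| Contrast (four contacts) | r = 0.1 | 0.3 | 0.5 | 0.7 |
|---|---|---|---|---|
| Group effect averaged over all four | 64.5% | 60.5% | 58.3% | 56.9% |
| Post-dose mean, unadjusted | 80% | 80% | 80% | 80% |
| Mean change from Visit 1 | 36.6% | 56.3% | 80.0% | 97.7% |
| Joint group-by-time test (3 df) | 24.3% | 39.9% | 64.5% | 92.9% |
| Post-dose mean adjusted for Visit 1 | 81.0% | 86.7% | 94.3% | 99.4% |

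With 30 daily scores plus Visit 1, and d reset so that the 30-score post-dose mean has 80% power, averaging over all 31 gives about 77% to 78% across the same r.

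**Step 5: which schedule fits the model?** An unstructured covariance on m times has m(m + 1)/2 parameters: 4 × 5/2 = 10 for four contacts and 31 × 32/2 = 496 for 31 daily times, against 104 enrolled subjects. The four-contact schedule suits the planned covariance better, but Section 13 describes daily scores. The documents do not settle which is analysed.

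**The case against.** A reader might infer that Section 14 dilutes any treatment effect on pain. The documents do not support that. The model includes a group-by-time term, so post-dose contrasts and changes from Visit 1, neither of which is attenuated, can be taken from it. Nothing says that the average over all times is what will be tested. If daily diary scores are analysed, even that average loses only about 3%.

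A reader might also infer that the baseline goes unused. That is too strong. A pre-dose score kept as a response in an unstructured model is a recognised approach: it is the natural reference in the group-by-time test, and it informs estimates when later scores are missing. What is missing is the covariate, or the equal-means constraint, that turns it into a baseline adjustment.

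Squaring the attenuation gives (4/3)² = 1.78 times the subjects. That ignores the smaller variance of a four-score mean; the multiplier stays at 1.52 to 1.70 for r from 0.2 to 0.6. Nor do the documents say that pain usually falls from presentation in both arms, and the point does not need it.

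Finally, the bracket in Section 14 largely repeats the assessment times in Appendix A and states no estimand, and the endpoint is secondary and unpowered. All of this stands and limits the point. It does not supply a baseline adjustment or name a test. The table shows that the unnamed choice of contrast matters, and Section 13 makes no multiplicity adjustment that would limit a choice made after the data are seen.

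**Conclusion.** The point holds as a free improvement. Visit 1 is listed as an on-treatment pain time although it is in effect pre-dose, and the model neither adjusts for it nor constrains the arms to be equal there. The loss that applies to any unadjusted post-dose comparison is one of precision: 4% to 36% of the variance of a single-time contrast for an assumed r of 0.2 to 0.6. Dilution is conditional on testing the average over all listed times: to 75% of a constant effect with four contacts (about 1.5 to 1.7 times the subjects under compound symmetry with the same r), or to about 97% with 30 daily scores plus Visit 1.

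The correlation, the constant effect and the equal SD are assumptions, since the documents give no pain parameters. That Visit 1 is pre-dose is an inference from the order of events in Section 9. The stone-passage analysis and the 104-subject sample size are not affected.

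**What to change.** - **Section 14:** name the Visit 1 FACES score as the pain baseline and list only post-dose times as endpoint times. Reconcile these with the daily scores in Section 13: state either the three contacts (Interim Follow-up #1, Interim Follow-up #2, Visit 2) or the post-dose diary days, and, if the latter, which diary day counts as the first post-dose score.
- **Section 13, use of Visit 1:** either add Visit 1 FACES as a covariate and take it out of the response vector, or keep it as a response with the two arms' means set equal at Visit 1. The second option retains subjects without a Visit 1 score and needs no imputation, so it agrees with the plan's rule on missing data. Mean imputation of a missing baseline covariate would conflict with that rule.
- **Section 13, test:** name one post-dose group contrast, for example the mean over the post-dose times, as the test of treatment.

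The score is already collected, so the cost is wording in two sections and minor analysis work.

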15. RISKS

There are risks to any medication. However, mirabegron is a FDA-approved medication and has passed rigorous trials for safety.

- A. Mirabegron:** Mirabegron is contraindicated in patients who have known hypersensitivity reactions to mirabegron or any component of the tablet. Mirabegron can increase blood pressure. Periodic blood pressure determinations are

recommended, especially in hypertensive patients. Mirabegron is not recommended for use in severe uncontrolled hypertensive patients (defined as systolic blood pressure ≥ 180 mm Hg and/or diastolic blood pressure ≥ 110 mm Hg).

Urinary retention in patients with bladder outlet obstruction (BOO) and in patients taking antimuscarinic medications for the treatment of OAB has been reported in post-marketing experience in patients taking mirabegron. A controlled clinical safety study in patients with BOO did not demonstrate increased urinary retention in Mirabegron patients; however, Mirabegron should be administered with caution to patients with clinically significant BOO. Mirabegron should also be administered with caution to patients taking antimuscarinic medications for the treatment of OAB.

Angioedema of the face, lips, tongue and/or larynx has been reported with Mirabegron. In some cases angioedema occurred after the first dose. Cases of angioedema have been reported to occur hours after the first dose or after multiple doses. Angioedema associated with upper airway swelling may be life threatening. If involvement of the tongue, hypopharynx, or larynx occurs, promptly discontinue Mirabegron and initiate appropriate therapy and/or measures necessary to ensure a patent airway.

Since Mirabegron is a moderate CYP2D6 inhibitor, the systemic exposure to CYP2D6 substrates such as metoprolol and desipramine is increased when co-administered with Mirabegron. Therefore, appropriate monitoring and dose adjustment may be necessary, especially with narrow therapeutic index drugs metabolized by CYP2D6, such as thioridazine, flecainide, and propafenone.

Most commonly reported adverse reactions over 2% and greater than with placebo) were hypertension, nasopharyngitis, urinary tract infection and headache.

Subjects will be monitored carefully for such side effects and should the subject feel uncomfortable continuing treatment, he will be allowed to discontinue participation in the study.

PREGNANCY: It is possible that the medicines used in this study could injure a fetus if the subject or partner becomes pregnant while taking them. Because of the potential risks involved, the subject or partner should not become pregnant while you are participating in this study.

If subject is sexually active or become sexually active and can get pregnant or can get the partner pregnant, the subject must agree to use one of the following forms of birth control every time the subject has sex from now until 3 months after stopping the study drug:

- * oral contraceptives ("the pill"),
- * intrauterine devices (IUDs),
- * contraceptive implants under the skin, or contraceptive injections,

* condoms with foam.

Should pregnancy occur while on this study, the subject must immediately notify the study personnel.

The investigator will assist in finding appropriate medical care. The investigator also may ask to be allowed to continue getting information about the pregnancy. The subject can choose not to provide this information.

- B.** Blood Draw: Inserting needles into veins for collecting blood may be uncomfortable. Risks include slight bruising at the puncture site, fainting, the formation of a small blood clot or swelling of the vein and surrounding tissue, bleeding from the site, and the remote possibility of infection at the site of the needle puncture. Fainting is usually harmless, of short duration, and typically produces feelings of weakness, sweating, slowing of the heart rate and an abnormal decrease in blood pressure. Care will be taken to avoid these complications.
- C.** Blood Pressure: Subjects may feel a slight discomfort while the band on the arm is tightened in order to take the reading.
- D.** Scans: CT scans, ultrasounds, and plain x-rays do not cause any physical discomfort. Anxiety in anticipating these procedures might be experienced. CT scans and plain x-rays subject patients to small amounts of radiation. In the field of radiation protection, it is commonly assumed that the risk for adverse health effects from cancer is proportional to the amount of radiation dose absorbed and the amount of dose depends on the type of x-ray examination. A CT examination with an effective dose of 10 millisieverts (abbreviated mSv; 1 mSv = 1 mGy in the case of x rays) may be associated with an increase in the possibility of fatal cancer of approximately 1 chance in 2000. This increase in the possibility of a fatal cancer from radiation can be compared to the natural incidence of fatal cancer in the U.S. population, about 1 chance in 5. In other words, for any one person the risk of radiation-induced cancer is much smaller than the natural risk of cancer. Nevertheless, this small increase in radiation- associated cancer risk for an individual can become a public health concern if large numbers of the population undergo increased numbers of CT screening procedures of uncertain benefit. It must be noted that there is uncertainty regarding the risk estimates for low levels of radiation exposure as commonly experienced in diagnostic radiology procedures.
- E.** Loss of Confidentiality: The loss of confidentiality regarding research information is a possibility, although, the risk is extremely small. The investigator and his/her research staff will make every effort to maintain the confidentiality.
- F.** Ureteroscopy with stent placement: Patients will have a small camera placed in their bladder. A smaller camera will be placed in the kidney which will be used to find the stone. If unable to introduce this smaller camera in the kidney a stent will be left to open up the ureter, the tube that drains the kidney and another attempt will be made

in a few weeks. The stone will be broken apart by a laser. The small fragments may be individually removed. An x-ray will be used for the procedure. A stent will be left in the kidney after the procedure and will be removed in clinic.

G. Questionnaires: Completing the questionnaires may cause some level of emotional discomfort due to the personal nature of the questions. The study doctor and staff will maintain a professional and caring attitude while administering the questionnaires.

16. ASSESSMENT OF SAFETY

A. Adverse Events Reporting

All adverse event (Severe Adverse Event (SAE), Unanticipated Event (UAE), or Adverse Event (AE) will be assessed by the Principal Investigator using the BCM PI Determination form. The IRB will be notified according to current rules, regulations, and procedures.

B. Serious Adverse Event Reporting

Within 24 hours of awareness of a serious adverse event, whether or not related to the study drug, the Investigator will complete and submit a Medwatch 3500A Form to FDA, containing all required information (reference 21 CFR 312.32). The Investigator will submit a copy of this MedWatch 3500A form to Astellas by either e-mail or fax, within the same timeframe. If submission of this SAE to FDA or Astellas or is not possible within 24 hours, the Investigator's local drug safety contact (IRB, etc.) should be informed by phone.

The SAE documentation, including the Medwatch 3500A Form and available source records should be emailed or faxed to:

Astellas Pharma Global Pharmacovigilance – United States
Email: [contact]
[contact]

The following minimum information is required:

- Study number/IIT regulatory identifier
- Subject number, sex and age
- The date of report
- A description of the SAE (event, seriousness of the event)
- Causal relationship to the study drug

Follow-up information for the event should be sent promptly (within 7 days) as necessary.

C. Additional safety analyses will be conducted in the safety population, defined as all subjects who receive at least one treatment with study drug.

Safety and tolerability will be assessed by evaluating physical, clinical laboratory tests, and reported AEs.

17. WITHDRAWAL OF SUBJECTS

Subjects for the study will be selected during screening based on the inclusion and exclusion criteria and clinical assessment listed below. Subjects will be discontinued from the study prematurely if:

- A. Unacceptable AEs considered by the investigator to be associated with use of the study drug occur
- B. The subject requests to be withdrawn from the study
- C. A need for concomitant medication prohibited by the protocol arises
- D. The Principal Investigator decides that it is in the subject's best interest
- E. The subject is significantly non-compliant with the protocol

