Subjects will be informed that they may also discontinue the study drug at any time if they would like to drop out of the trial and they may do so by contacting [name] or designee. Subjects will be informed to contact [name] or designee if they believe that they have passed their ureteral stone before discontinuing therapy. Subjects will be told to bring their medication bottles when they return to the clinic.

In the event that a subject has additional pain, discomfort, or other symptoms that may be related to their ureteral stone they may follow-up for an unscheduled visit to either the emergency department or the Urology clinic. The subject will be treated according to standard of care and information regarding their visit will be collected. If the subject must undergo an emergent procedure for their stone they will be determined to have failed therapy but will remain in the study to evaluate the study drug to reduce stent pain. Subjects that fail therapy early will undergo Visit 3 and will be evaluated at Visit 4 for the removal of their stent. Subjects will remain in the study for all outcome measurements if they do not require surgical intervention.

Interim Phone Follow-up #1 – (7 Days ± 3 days post-Visit 1)

The research study staff will contact the subject by phone approximately 7 days after Visit 1. Research staff will assess ureteral pain, medication/strainer compliance, and adverse events. Research staff will also identify whether or not the subject subjectively or objectively has passed their ureteral stone. The research staff will also answer any questions that the subject may have during this follow-up event.

Interim Phone Follow-up #2 – (21 Days ± 3 days post-Visit 1)

The research study staff will contact the subject by phone approximately 21 days after Visit 1. Research staff will assess ureteral pain, medication/strainer compliance, and adverse events. Research staff will also identify whether or not the subject subjectively or objectively has passed their ureteral stone. The research staff will also answer any questions that the subject may have during this follow-up event. The research staff will also remind the subjects to bring in their medication bottles to Visit 2 (see below).

Visit 2 – Urology Clinic (30 days ± 5 days post-Visit 1)

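### Section 17 takes patients out of the study, not only off drug; their day-30 stone status is then not collected, and no as-randomised primary analysis set is named

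*Combined protocol and SAP*

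**What the plan says.** **Withdrawal.** Section 17 lists five reasons under the lead-in "Subjects will be discontinued from the study prematurely if". Three of them concern treatment or adherence rather than the patient's wish to leave:
- item A: "Unacceptable AEs considered by the investigator to be associated with use of the study drug occur"
- item C: "A need for concomitant medication prohibited by the protocol arises"
- item E: "The subject is significantly non-compliant with the protocol"

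**Follow-up.** Two further places link stopping drug with leaving, both as a patient's choice. Section 9 (Visit 1) tells patients that "they may also discontinue the study drug at any time if they would like to drop out of the trial". Section 15 says that "should the subject feel uncomfortable continuing treatment, he will be allowed to discontinue participation in the study". Section 9 also has a retention rule in its paragraph on unscheduled visits: "Subjects will remain in the study for all outcome measurements if they do not require surgical intervention". The same paragraph classifies emergencies: "If the subject must undergo an emergent procedure for their stone they will be determined to have failed therapy". Visit 2 in Section 9 provides imaging and clinic review of stone status at about day 30 as standard of care.

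**Analysis.** Section 12 describes the primary comparison by the treatment patients received. Section 13 compares the study groups by Fisher's exact test. The only population defined is the safety population in Section 16. Section 13 rules out imputation of missing data, in a sentence that follows the description of the pain model.

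**The concern.** Items A, C and E are ordinarily reasons to stop a drug, not to stop measuring the outcome. Section 17 does not make that distinction, and no later text tells staff to find out whether a withdrawn patient's stone had passed by day 30.

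Item A can depend on arm, because it requires an adverse event attributed to study drug. Item C could depend on outcome, if the medication is needed because the stone persists. Losses of either kind are not random with respect to the primary comparison. The 15% attrition allowance in Section 11 protects precision, not comparability.

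The analysis text does not repair this. If the no-imputation sentence covers the primary test, withdrawn patients without a status drop out of it. If it does not, there is no rule for them at all.

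**Working it through.** **1. The plan's own figure.** Inputs from Sections 11 and 13: placebo rate 50%, difference 0.30 (so 50% v 80%), two-sided alpha 0.05, Fisher's exact test, 45 per group, 15% attrition, 104 enrolled. Power is the sum, over all pairs of passer counts, of the product of the two binomial probabilities wherever Fisher p ≤ 0.05.
- 45 v 45: 81.5%, which agrees with the stated 80%.
- 90 × 1.15 = 103.5, rounded up to 104, or 52 per arm.
- 15% of 52 = 7.8, taken as 8 lost per arm, leaving 44 v 44: power 80.2%.

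**2. Assumptions for the illustration.** 52 per arm and 8 lost per arm. Of the 8, k leave under Section 17 and share one outcome; the other 8 − k pass at their arm's rate. The documents give no value for k; 3 and 4 are assumed. Mixed rates within an arm are treated as one binomial.

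**3. No true effect (50% in both arms).** If an arm loses k non-passers, its completer rate is (26 − 0.5(8 − k))/44 = (22 + 0.5k)/44. If it loses k passers, the rate is (26 − k − 0.5(8 − k))/44 = (22 − 0.5k)/44.

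| Selective loss | Placebo rate | Mirabegron rate | Rejection |
|---|---|---|---|
| None | 0.500 | 0.500 | 2.5% |
| 3 mirabegron non-passers | 0.500 | 0.534 | 3.3% |
| 4 mirabegron non-passers | 0.500 | 0.545 | 3.9% |
| 3 mirabegron non-passers and 3 placebo passers | 0.466 | 0.534 | 5.7% |
| 4 mirabegron non-passers and 4 placebo passers | 0.455 | 0.545 | 8.4% |

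Unequal losses matter too. With 10 mirabegron and 6 placebo patients lost, and 4 of the 10 selective non-passers, the mirabegron rate is (26 − 0.5 × 6)/42 = 0.548 against 0.500 in 46 placebo patients. Rejection is then 5.1%.

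**4. True 50% v 80%, 44 v 44.** The mirabegron completer rate after losing k non-passers is (41.6 − 0.8(8 − k))/44 = (35.2 + 0.8k)/44.

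| Selective loss | Placebo rate | Mirabegron rate | Power |
|---|---|---|---|
| None | 0.500 | 0.800 | 80% |
| 3 placebo non-passers | 0.534 | 0.800 | 70% |
| 4 placebo non-passers | 0.545 | 0.800 | 66% |
| 3 non-passers in each arm | 0.534 | 0.855 | 88% |
| 4 non-passers in each arm | 0.545 | 0.873 | 90% |

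**5. Analysing everyone.** If s mirabegron patients stop drug and pass at the placebo rate, the arm's rate with all 52 followed is (0.8(52 − s) + 0.5s)/52.
- s = 0: rate 0.800, power 87%.
- s = 3: rate 0.783, power 82%.
- s = 4: rate 0.777, power 80%.
- s = 7.8 (15%): rate 0.755, power about 72%.

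If only the 3 or 4 Section 17 losses per arm are recovered, the mirabegron rate is (0.8 × 44 + 0.5s)/(44 + s). That is 0.781 with 47 per arm (power 76%) or 0.775 with 48 per arm (power 74%).

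**The case against.** **Section 9 already retains patients.** Its retention rule covers patients who need no surgery. But it sits in the paragraph on unscheduled visits and does not mention Section 17. Read broadly, it keeps a patient whom item C removes, so the two sections conflict and must be reconciled.

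**As-randomised analysis is the natural reading.** Section 13 compares study groups, and the treated population in Section 16 is confined to safety. That is reasonable, but it does not say whether a withdrawn patient without a status counts in the denominator.

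**The outcome-dependent route is thin.** This stands in part. The documents as supplied list no prohibited medications for the expectant period. The explicit bar on prescribing comes at Visit 3, after the day-30 outcome, and the drug classes in Section 6 are entry exclusions. Loss of status through item C is therefore an inference.

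**Sections 9 and 15 describe voluntary exit.** This stands. A reader might infer that they too force removal of anyone who stops drug; they do not. They only fail to offer stopping drug while staying in follow-up.

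**The fix may cost power.** This also stands. Recovering only the Section 17 patients can give 74% to 76%, against 80% for completers. The completer figure, however, assumes that the losses are unrelated to outcome, which is the point in doubt.

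**Conclusion.** The point holds and should be fixed. As written, Section 17 ends study participation for reasons that can depend on arm and possibly on outcome. Day-30 status is not sought afterwards, and the primary analysis set and missing-data rule are not settled.

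The size is not known. All selective-loss figures rest on assumed counts, and the 15% in Section 11 is general attrition, not a forecast of Section 17 withdrawals.

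Two firmer readings are tempting, and neither is supported:
- A reader might infer that the false-positive risk stays below 5% when only a few patients are withdrawn. That holds for equal losses with selection in the mirabegron arm alone. It fails at 3 and 3 in opposite directions (5.7%) and at 10 v 6 losses with 4 selective (5.1%). No flat bound can be given.
- A reader might infer that the design favours mirabegron or badly inflates the error. The documents give no split of withdrawals by arm or outcome, and selective loss can lower power as easily as raise it.

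Some pages were removed from the documents as supplied and could not be checked.

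**What to change.** **Section 17.** Leave the triggers unchanged, but separate stopping study drug from leaving the study. Unless consent is withdrawn, keep the phone calls and record the standard-of-care Visit 2 stone status where available. Reconcile Section 17 with the retention rule in Section 9 and with the voluntary-exit wording in Sections 9 and 15.

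**Sections 12 and 13.** Define the primary analysis as all randomised patients by assigned arm, with an emergent procedure counted as failure, as Section 9 already provides. State whether the no-imputation rule covers the primary test. Add one simple sensitivity analysis for patients whose status is still missing.

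**Cost.** Protocol wording and a few calls or chart checks, with no added visit or imaging. Some non-compliant patients may still not attend Visit 2. Counting patients who stopped drug can dilute the effect: under the assumptions in step 5, power with all 52 per arm followed stays at about 80% with 4 mirabegron patients stopping. Recheck the sample size if more are expected, or if many other losses will remain.
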